Clinical trials of intranasal insulin in AD have demonstrated therapeutic effects involving memory, attention and cognition without significantly altering serum insulin or glucose levels. A clinical trial consisting of 26 memory impaired subjects (13 with AD and 13 with mild cognitive impairment) and 35 normal controls showed that IN insulin 20 IU or 40 IU resulted in improvements on two declarative memory tasks compared to placebo within 15 minutes of drug administration (29). IN insulin administered at 20 IU resulted in greater story recall whereas doses at 40 IU more favorably improved word list recall. There was no impact on IN insulin on serum glucose or insulin levels. Another study of 24 early AD/mild cognitive impairment subjects showed that 20 IU BID of intranasal insulin resulted in sustained benefit in over a 21 day period (30). Furthermore, IN insulin induced favorable changes in the serum amyloid-beta 40/42 ratio while having no impact on systemic glucose or insulin levels. Most recently, Craft and colleagues have shown improved memory and function as represented by the ADAS-Cog and ADCS-ADL, respectively in AD patients treated during a four month clinical trial (31). These changes in memory and function were associated with favorable changes in CSF tau and tau-Ab42 ratio. Additionally, IN insulin minimized progression in loss of cerebral hypometabolism as measured by FDG-PET.

Therapeutic response to IN insulin may be modified by both insulin type as well as ApoE4 carrier status. A study of 38 normal subjects showed that rapid-acting insulin aspart (Insulin NovoLog HM, Novo Nordisk) resulted in greater declarative memory improvements compared to regular insulin over 8 an week period (32). Additional clinical trials have suggested memory benefits associated with IN insulin are diminished among ApoE4 carriers diagnosed with AD (29).

Glulisine is a rapidly absorbed insulin analogue lacking the zinc ingredient commonly found in insulin formulations. This analogue differs from human insulin in that the amino acid asparagine at position B3 is replaced by lysine and the lysine in position B29 is replaced by glutamic acid. For this study, we have chosen glulisine due to prior speculation that zinc-containing compounds may be toxic to olfactory neurons (33, 34) as well as prior studies demonstrating improvements in declarative memory with RA compared to regular insulin.

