5. STUDY DESIGN

This study is a single center, phase II randomized, double-blind, placebo-controlled clinical trial designed to assess the efficacy of intranasally (IN) administered glulisine versus placebo in patients with aMCI and probable mild AD.

After written informed consent has been obtained from the subject and family member/caregiver, subjects will be screened to assess study eligibility based on study inclusion/exclusion criteria. Subjects who are eligible at the end of the screening visit (Visit 1) will be scheduled for a baseline visit (visit 2). During the baseline visit, subjects will undergo neuropsychological testing with the ADAS-Cog 13 battery and supplemental tests including the Trailmaking Test Parts A & B, Digit Span, Controlled Oral Word Association Test, Animal Naming, and WMS logical memory to establish a baseline. Repeat cognitive assessments will be performed at 12 and 24 weeks. Patients will also be assessed on two additional measures for olfaction (Alberta smell test) and sleep measures (Sleep Questionnaire and ESS) at baseline, 12 weeks, and 24 weeks. Patients enrolled in the AD biomarker substudy will undergo a baseline FDG-PET scan and CSF biomarkers (Abeta42, tau, phosphotau) at baseline and 24 weeks.

A total of n=90 subjects will be randomized to receiving either IN glulisine (n=45) or placebo (n=45) two times daily (morning and evening, separate by at least 8 hours). In addition, subjects will be block randomized based on ApoE4 status, presence of non-insulin dependent diabetes, and MOCA score (18-22 vs. 23-27). Subjects will receive either 0.2 ml IN insulin (20 IU) (0.1ml/10 units IN in each nostril) or placebo administered two times daily over a 6 month period.

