5.1. Outcome Measures

Neuropsychological, functional, and depression batteries will be performed at screen/baseline, Visit 7 and at Visit 10 (refer to section 7.4 for full description) to assess primary endpoint. A subset of subjects will undergo testing for CSF biomarkers (Abeta42, tau, phosphotau) and FDG-PET imaging at baseline and Visit 10 to address exploratory endpoints.

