7.1.2. Visit 2; Baseline Visit

The following procedures will be performed at this visit:

- Review Inclusion/Exclusion Criteria.
- Collect vital signs and weight.
- Collect concomitant medication information and record AEs/SAEs.
- Neuropsychological testing with ADAS-Cog 13 and supplemental cognitive assessments.
- Administer CDR
- Administer Columbia-Suicide Severity Rating Scale (C-SSRS).
- Administer Functional Assessment Questionnaire (FAQ).
- Administer Alberta Smell Test.
- Administer sleep measures (Sleep questionnaire and ESS)
- Study Drug administration training.
- Hypoglycemia rescue training.
- Sub-study PET scan. For participating subjects, scan will be obtained within 1 week (\pm 3 days).
- Sub-study LP/ CSF. For participating subjects, procedure will be performed within 1 week (\pm 3 days).

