7.1.7. Visit 7; Treatment and Adherence; (Week 12)

Following procedures will be performed at this visit.

- Collect vital signs and weight.
- Collect concomitant medication information and record AEs/SAEs.
- Neuropsychological testing with ADAS-Cog 13 and supplemental cognitive assessments.
- Administer CDR.
- Administer FAQ.
- Administer GDS.
- Administer C-SSRS.
- Administer sleep measures (Sleep questionnaire and ESS)
- Administer Alberta smell test
- Review training of study drug administration.
- Study drug dispensing/diary.

- Visit 8 will be scheduled within 1 month (± 3 days).

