7.1.10. Visit 10; 6 month follow-up (Week 24)

Following procedures will be performed at this visit.

- Collect vital signs and weight.
- Collect concomitant medication information and record AEs/SAEs.
- Neuropsychological testing with ADAS-Cog 13 and supplemental cognitive assessments.
- Administer CDR.
- Administer FAQ.
- Administer GDS.
- Administer Alberta smell test
- Administer sleep measures (Sleep questionnaire and ESS)
- Obtain repeat FDG-PET study in subgroup. Scan will be obtained within 1 week (± 3 days).
- Obtain repeat spinal fluid analysis in subgroup. Procedure will be performed within 1 week (± 3 days).
- Visit 11 scheduled within 1 month (± 7 days).

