insulin on each measure will be tested on the intervention arm*week interaction. Efficacy measures with corresponding 95% confidence intervals and p-values will be reported.

Exploratory measures of sleep (Sleep Questionnaire and ESS) and biomarkers (CSF Abeta, tau, and phosphotau) will follow the same approach as for the primary outcomes. Two multivariate linear mixed-effects regression models will be fit with change in either sleep or biomarker measures from baseline to visit 7 and baseline to visit 10 as the outcome variables. The efficacy of IN insulin on sleep will be tested on the intervention arm*week interaction. Efficacy measures for composite sleep decline with corresponding 95% confidence intervals and p-values will be reported.

Exploratory PET metabolism will be measured in four cortical ROIs primarily affected by AD: precuneus, posterior cingulate, and bilateral parietotemporal. A multivariate regression model will again be applied to the imaging outcome measures. Specifically, standardized change in posterior cerebral metabolism in the four ROIs from baseline to 6 months will serve as the outcomes. Intervention arm, age, and baseline test scores will be used as fixed effects. Tests of assumptions and interpretation will be similar to that described for primary outcomes. Overall cerebral metabolism and metabolism at each of the four cortical ROIs efficacy measures with corresponding 95% confidence intervals and p-values will be reported.

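### The CSF biomarker model relies on a visit-7 change that is never collected, so its arm-by-week test cannot be estimated, and the treatment effect across the three markers is left undefined

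*Combined protocol and SAP*

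**What the plan says.** Section 12.2 states that sleep and "biomarkers (CSF Abeta, tau, and phosphotau) will follow the same approach as for the primary outcomes". It then specifies two multivariate mixed models, one for sleep and one for biomarkers, with "change in either sleep or biomarker measures from baseline to visit 7 and baseline to visit 10 as the outcome variables".

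The primary approach, set out earlier in Section 12.2, has fixed effects for arm, week, arm by week, age and baseline score. Efficacy is tested on arm by week, and a composite effect is reported. In the sleep and biomarker paragraph, the sentences naming the test and the composite mention sleep only. No test or estimand is stated for the biomarkers.

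The collection schedule is consistent wherever it appears:

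- Section 5: "CSF biomarkers (Abeta42, tau, phosphotau) at baseline and 24 weeks".
- Section 5.1: "A subset of subjects will undergo testing for CSF biomarkers (Abeta42, tau, phosphotau) and FDG-PET imaging at baseline and Visit 10".
- Section 7.1.2 (Visit 2): "Sub-study LP/ CSF. For participating subjects, procedure will be performed within 1 week".
- Section 7.1.7 (Visit 7): the list includes "Neuropsychological testing with ADAS-Cog 13 and supplemental cognitive assessments" together with functional, mood, sleep and smell measures, but no lumbar puncture.
- Section 7.1.10 (Visit 10): "Obtain repeat spinal fluid analysis in subgroup".

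On the direction of the markers, the only indication is in Section 1.1, which reports "favorable changes in CSF tau and tau-Ab42 ratio" in an earlier trial.

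**The concern.** The planned biomarker analysis needs an outcome at a visit where no spinal fluid is taken, and its inherited test compares arms across two times when only one exists. Whoever runs it must replace it with something else, and that choice would be made after the data are in.

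The choice matters because three markers are involved. One common arm effect, marker-specific effects and a joint test answer different questions and have different power. If one effect is fitted to raw changes, the markers with the largest numerical spread dominate, and markers that improve in opposite directions offset each other. Participants in this sub-study undergo two lumbar punctures for the objective, so its analysis should be fixed in advance.

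**Working it through.** **No figure to reproduce.** The documents give no sample size, effect, SD, correlation or power for CSF. The check is therefore one of estimability, followed by an illustration under stated assumptions.

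**Step 1: can the planned test be estimated?** Take the Section 12.2 fixed effects: intercept, arm, week, arm by week, age, baseline value (6 columns).

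| Visits with a change score | Columns | Rank |
|---|---|---|
| 7 and 10 (as the model assumes) | 6 | 6 |
| 10 only (as CSF is collected) | 6 | 4 |

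With one post-baseline time, week is constant and aliased with the intercept, and arm by week is aliased with arm. Two terms are lost, including the one to be tested. The mixed model's handling of missing data does not help, because visit-7 CSF is absent for everyone in both arms. Only the week-24 arm effect can be estimated. This step needs no assumption.

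**Step 2: what if one common arm effect is fitted?** Suppose benefit means Abeta42 up and tau and phosphotau down, each by d SD. This direction is inferred from the ratio in Section 1.1. The average effect on standardised, unsigned values is

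(d - d - d)/3 = -d/3,

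one third of the per-marker effect. It reaches zero only if the Abeta42 effect equals the sum of the other two. With tau and phosphotau at -0.8 SD each, the average for Abeta42 at 0, 0.4, 0.8, 1.2 and 1.6 SD is -0.53, -0.40, -0.27, -0.13 and 0.

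**Step 3: illustrative power.** Assume d = 0.6, tau-phosphotau correlation 0.8, Abeta42 correlation -0.3 with each, 20 per arm, and a two-sided 0.05 t-test on the mean of the three standardised changes.

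- Unsigned: effect 0.6/3 = 0.20. Variance [3 + 2(0.8 - 0.3 - 0.3)]/9 = 3.4/9 = 0.378, SD 0.615. Noncentrality 0.20/(0.615 × √(2/20)) = 1.03. Power about 17%.
- Abeta42 sign-reversed: effect 0.60. Variance [3 + 2(0.8 + 0.3 + 0.3)]/9 = 5.8/9 = 0.644, SD 0.803. Noncentrality 0.60/(0.803 × √(2/20)) = 2.36. Power about 63%.

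| Per arm (assumed) | Unsigned | Sign-aligned |
|---|---|---|
| 15 | 14% | 51% |
| 20 | 17% | 63% |
| 30 | 24% | 81% |

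Varying the Abeta42 correlation from -0.3 to 0.3 at 20 per arm gives 12 to 17% unsigned and 63 to 85% aligned. Varying d at correlation -0.3 and 20 per arm gives 10% against 34% at d = 0.4, and 27% against 87% at d = 0.8.

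**Step 4: raw scales.** With d = 0.8 and assumed SDs for Abeta42, tau and phosphotau of (150, 100, 20), the pooled value is 0.8 × (150 - 100 - 20)/3 = +8.0. With (200, 300, 25) it is 0.8 × (200 - 300 - 25)/3 = -33.3. So the sign itself depends on the scales.

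**Step 5: comparison with PET.** The next paragraph of Section 12.2 uses standardised change from baseline to 6 months, has no week term, and reports each region alongside the overall effect. The CSF text specifies none of this.

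**The case against.** The strongest reply is that a single pooled CSF effect is never stated. It follows only from carrying over the primary approach, and a multivariate model can be coded with marker-specific effects. A conventional joint test of the arm effect (Hotelling type) does not depend on marker sign or scale. Under the Step 3 assumptions it has about 34%, 46% and 66% power at 15, 20 and 30 per arm. Section 12.2 also allows log-transformation with percent-change effects, which would reduce dominance by scale if it were inherited, though it would not change sign. All of this stands. It makes the attenuation conditional on one reading, and it shows that the estimand is open.

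A reader might infer that a real CSF effect would cancel, or that the CSF objective will probably be reported as null. The documents support neither. Equal standardised effects shrink to one third, and complete cancellation needs a particular balance of sizes or scales. Power is modest in any case: a single 0.6 SD marker analysed alone has about 36%, 46% and 63% at 15, 20 and 30 per arm.

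Nor do the documents state a favourable direction for Abeta42 or phosphotau; the ratio supports an inference about Abeta42 and no more.

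The Study Visit Table mentioned in the assessments section was not in the text available for review. Every schedule section that could be read agrees. Nothing in the reply rescues the visit-7 outcome or the arm-by-week test.

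**Conclusion.** The biomarker analysis is wrong as written: it uses a visit-7 CSF change that is not collected, and the inherited arm-by-week test cannot be estimated. This rests on the documents alone.

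The second part is conditional. If the model is read as one common arm effect on unstandardised, unsigned markers, the effect could be strongly attenuated. The power figures only illustrate that reading, and they depend on an assumed effect size, correlations, sub-study size and marker directions.

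The sleep composite has a related gap. Hours of sleep, sleep latency (Section 7.4.13) and the ESS score (Section 7.4.14) share neither a unit nor a direction, and no common scoring is given. Sleep is collected at both visits, so its arm-by-week term can be estimated.

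This is a minor correction to exploratory endpoints. No primary or secondary conclusion depends on it.

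**What to change.** In Section 12.2:

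1. Remove visit 7, and the week and arm-by-week terms, from the CSF analysis.
2. For each of Abeta42, tau and phosphotau, fit week-24 change on arm, age and that marker's baseline value. Report each arm effect with its 95% confidence interval, as is already planned for each PET region.
3. If an overall CSF test is wanted, pre-specify a composite of standardised changes with Abeta42 sign-reversed, and state the favourable direction of each marker.
4. State the planned size of the sub-study.
5. Before forming the sleep composite, put its items on a common scale and direction.

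The cost is SAP wording only, ideally before unblinding. No visit, sample or procedure changes.

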7.4.13 Sleep Questions

A set of 4 questions will be asked to the caregiver/spouse that looks at areas of sleep quality including sleep duration, sleep latency and sleep efficiency for the past month. The questions address the patient's usual bedtime and wake-up time, as well as how long it takes to fall asleep and how many hours of sleep are obtained per night. The caregiver will answer these questions for the subject.

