7.4.14 Epworth Sleepiness Scale (ESS)

Epworth sleepiness scale (ESS) is a simple self-administered questionnaire that is widely used to measure the daytime sleepiness of an individual (52). It has 8 standardized questions that assess the likelihood of a subject dozing off or falling asleep (on a scale of 0-3) in daily living situations. A total of 0-24 score can be obtained. Excessive daytime sleepiness is assumed if a subject reaches a score of 10 and above. The caregiver will answer these questions for the subject.

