12.2. Statistical Analysis of Efficacy Outcomes

Previous research has shown that the primary outcomes (ADAS-Cog 13, CDR-SOB, and FAQ) to be highly correlated. Therefore, to increase power and account for this correlation, the primary analysis will be a multivariate, linear mixed-effects regression. Specifically, the change in cognition and function measures between baseline and week 12 and between baseline and week 24 will serve as the primary outcome variables. We will include intervention arm, intervention week, intervention arm*week, age, and baseline test scores as fixed effects. The efficacy of intranasal (IN) insulin on cognition and function will be tested on the intervention arm*week interaction. Age and baseline test scores are included because of the possibility of unequal baseline values. Random intercept effects will be included to account for the nested structure of the data, multiple outcomes and observation points.

First, the assumptions of such a model will be verified. That is, the dependent variables will be tested for: (1) multivariate normality, (2) homoscedasticity, (3) equality of covariance matrices, and (4) independent observations. These outcome variables have been analyzed after log-transformation in previous studies because they have a distribution skewed to the right. We will confirm that this transformation is suitable for our study. If outcome variables are log-transformed, efficacy measures will correspond to percent change of cognitive outcomes.

To protect against type I error, efficacy of IN insulin will be considered if an overall cognitive decline is observed relative to placebo. Efficacy measures for composite cognitive and functional decline with corresponding 95% confidence intervals and p-values will be reported.

For the analysis of secondary cognition and function measures (Digit Span, Trailmaking, COWAT, Animal Naming, and WMS), secondary mood measure (GDS), and exploratory smell measure (AST) we will follow the same approach as for the primary outcomes. We have not included these tests as primary endpoints because they measure more specific effects of AD language, memory, mood, or olfaction impairment and, therefore, may be less sensitive to overall cognitive change in MCI/AD patients. Each outcome measure will be tested in its own linear mixed-effects regression model with measures from baseline to week 12 and baseline to week 24 as the outcome variables. The efficacy of IN

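### The sleep composite in section 12.2 has no stated direction or scaling, although its components improve in opposite directions and no item-level test is planned

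*Combined protocol and SAP*

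**What the plan says.** Section 3.3 makes the effect on sleep an exploratory objective, and Table 2 in section 7.4 schedules the Sleep Questionnaire and ESS at visits 2, 7 and 10.

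The analysis is in section 12.2:

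- Approach: "Exploratory measures of sleep (Sleep Questionnaire and ESS) and biomarkers (CSF Abeta, tau, and phosphotau) will follow the same approach as for the primary outcomes".
- Model: "Two multivariate linear mixed-effects regression models will be fit with change in either sleep or biomarker measures from baseline to visit 7" (and from baseline to visit 10).
- Test: "The efficacy of IN insulin on sleep will be tested on the intervention arm*week interaction".
- Output: "Efficacy measures for composite sleep decline with corresponding 95% confidence intervals and p-values will be reported".

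The fixed effects of the primary model, which sleep inherits, are given as: "We will include intervention arm, intervention week, intervention arm*week, age, and baseline test scores as fixed effects". The list has no indicator for which outcome a row belongs to, and no outcome-by-arm term.

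On the inputs, section 7.4.13 says that the caregiver answers four questions, covering "usual bedtime and wake-up time, as well as how long it takes to fall asleep and how many hours of sleep". They are meant to address "sleep quality including sleep duration, sleep latency and sleep efficiency for the past month". For the ESS, scored 0 to 24, section 7.4.14 fixes the direction: "Excessive daytime sleepiness is assumed if a subject reaches a score of 10 and above".

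**The concern.** The model is borrowed from ADAS-Cog 13, CDR-SOB and FAQ, and section 12.2 justifies pooling those three by their high correlation. No such argument is made for sleep, and the sleep measures do not point one way. Longer latency and a higher ESS are worse. Fewer hours slept is worse on the usual reading, and so is lower efficiency if it is derived. Units are minutes, hours, a ratio and points.

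A single arm effect shared across such items is an average of differences with opposing signs. A drug that helped sleep on every item could produce a composite that is small, or whose sign follows the item with the largest numbers. With only the composite tested, the exploratory sleep objective would have no item-level treatment comparison to fall back on.

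**Working it through.** **No figure to reproduce.** The plan states no effect size, SD, correlation or power for sleep. The arithmetic below is illustrative.

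**Inputs from the document:** 45 per arm (section 12.4); two-sided 0.05 (section 12.1); item directions as above.

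**Assumed:** a true benefit of 0.4 SD on each directional item; items standardised; correlation ρ of 0 or 0.3 between directional items once coded the same way; equal weights; a two-sample t-test on the subject mean at one visit. The planned test is the arm-by-week interaction over weeks 12 and 24, so these are not its power figures.

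**Formula.** Composite effect = mean of the signed item effects ÷ SD of the subject mean. For k items coded the same way, the SD is √[(1 + (k − 1)ρ)/k]. Power comes from the noncentral t with 88 degrees of freedom and noncentrality effect × √(45/2).

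**1. Four derived items, natural signs** (duration and efficiency up, latency and ESS down): mean = (0.4 + 0.4 − 0.4 − 0.4)/4 = 0. Rejection rate 5%, the type I error.

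**2. The same four items, aligned:** mean = 0.4.
- ρ = 0: SD = √(1/4) = 0.50; effect 0.80; power 96%.
- ρ = 0.3: SD = √(1.9/4) = 0.689; effect 0.58; power 78%.

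**3. Five raw items, natural signs** (bedtime and wake time unaffected and uncorrelated with the rest; latency −0.4, hours +0.4, ESS −0.4): mean = −0.4/5 = −0.08. In natural signs, hours slept correlates negatively with latency and ESS.
- ρ = 0: SD = √5/5 = 0.447; effect 0.18 in absolute size; power 13%.
- ρ = 0.3: variance of the sum = 5 + 2(0.3 − 0.3 − 0.3) = 4.4; SD = √4.4/5 = 0.420; effect 0.19; power about 15%.

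**4. One item in its own model,** on the same simplified test: effect 0.40; power 47%.

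**5. Without standardisation** the result turns on units. Take invented changes of 0 in bed and wake times, −10 minutes in latency, +0.5 hours slept and −2 ESS points: (0 + 0 − 10 + 0.5 − 2)/5 = −2.3, nearly all of it latency. Take −15 minutes of latency, +17 minutes slept and −2 ESS points: (0 + 0 − 15 + 17 − 2)/5 = 0. Both sets describe better sleep throughout.

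**Does any other text supply the missing rule?** No. Standardised change is specified in section 12.2 for the PET regions only. The log-transformation check would put outcomes on a percent scale but would not align their direction. PET also gets a result per region, and the secondary tests and the Alberta Smell Test each get their own model. Sleep has neither safeguard.

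**The case against.** The best defence is that section 12.2 specifies no averaging rule. A multivariate model can carry outcome-specific arm effects, and the word decline implies that items are oriented towards worse before fitting. An analyst could do all of this consistently with the text. That is fair, but the listed fixed effects contain no outcome-by-arm term, and a composite is the only inferential sleep output named. The sensible reading has to be supplied by the analyst.

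Four stronger readings are tempting, and the documents do not support them:

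- **That clock times are pooled.** Section 12.2 names only the questionnaire and ESS. Bed and wake times may serve solely to derive efficiency. If they are entered raw, they have no worse direction and can wrap at midnight, but that is conditional. The main point survives either way, because hours slept, or duration and efficiency if derived, still run opposite to latency and ESS.
- **That a benefit cancels to zero.** Exact cancellation needs equal standardised effects, two each way. With latency, hours and ESS alone, the same assumptions give −0.4/3 = −0.13 rather than 0.
- **That sleep results would be uninterpretable or the objective unanswered.** Section 12.1 promises central tendency and spread by treatment group for each outcome variable. If the items are the outcome variables, their directions will be visible by arm, though without a test.
- **That the power figures describe the trial.** They describe a simpler test under assumed effects.

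**Conclusion.** The concern holds in a limited form. The plan tests sleep with one effect and reports one composite, without saying which variables enter, how they are signed or how they are scaled, while the natural directions conflict. Followed as written, the composite can understate a real benefit or be governed by one item's units, and its sign need not show which way sleep changed.

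Under the assumptions above, the loss runs from 78-96% power when aligned to 5% for four derived items in natural signs, with about 13-15% for five raw items. The size depends on equal 0.4 SD effects and equal weights, neither of which the documents give. The existence of the gap does not depend on them.

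This is a minor point. Sleep is exploratory, the primary conclusion is unaffected, and no data would be lost.

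**What to change.** In section 12.2, before unblinding:

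- Derive three variables from the four answers: sleep duration (hours), latency (minutes) and efficiency (hours slept divided by time in bed). Code clock times so that midnight does not wrap, and use them only to derive efficiency.
- Analyse each of these, and ESS, in its own mixed model, as already planned for the Alberta Smell Test, with an estimate and 95% confidence interval.
- Either drop the composite, or keep it on standardised scores all coded so that higher means worse, reported beside the item results.

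The cost is a few lines of SAP text and four small models in place of one. The real downside is four p-values instead of one; label them exploratory and unadjusted. No new data, visits or participants are needed.
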